The neutral effect on the cardiovascular system is particularly important in the acute and traumatic setting when patients are often hypotensive. However, there are some differences and disadvantages in the two medications. Etomidate induces sedation by enhancing the effect of GABA, an inhibitory neurotransmitter, resulting in inhibition of excitatory stimuli. Etomidate lacks analgesic effects and has been shown to cause adrenal suppression, of which the long term significance still remains uncertain. Ketamine is a non-competitive N-methyl-D-aspartate (NMDA) antagonist and a weak opioid agonist which results in both amnestic and analgesic properties. It is also a dissociative anesthetic and can cause profound hallucinations. There are also historical reports of ketamine causing an elevation of ICP, although newer research has not shown that effect. Due to all of these factors and limited data to support ketamine as an equal or superior alternative to etomidate, it has been difficult to clearly recommend one agent over the other for RSI.

Previous literature has evaluated the hemodynamic effects of etomidate and ketamine during RSI but these studies have been retrospective in nature.

A 2013 retrospective study by Price et al. did not find a significant difference between ketamine and etomidate in hemodynamics at any of the five post-intubation vital sign assessments. We recently conducted a retrospective comparative study on the hemodynamic effects of the two medications in the pre-hospital setting at New Hanover Regional Medical Center. There were more patients in the etomidate group to experience a decrease in SBP from pre-RSI to 15 minutes post-RSI, although the difference was not significant. We also discovered a lower SBP trend post-RSI with etomidate among the trauma and elderly population. This study was limited by the number of patients that received ketamine and was therefore underpowered.

A 2017, retrospective study was published with 968 adult trauma patients undergoing RSI in the ED with either etomidate or ketamine and results did not reveal a difference in patient-centered outcomes between the two drugs including hospital mortality, ICU-free days, ventilator-free days, vasopressor-free days, and transfusion requirements.

A prospective, randomized trial is needed to determine the superiority of one induction agent over another during this life saving measure.

AIM(S) OF STUDY:

The aim of this study is to investigate the hemodynamic effects of ketamine and etomidate in the setting of rapid sequence intubation.

OBJECTIVES:

The objective of this study is to determine if ketamine or etomidate has a better hemodynamic profile in patients undergoing rapid sequence intubation.

HYPOTHESIS:**Primary Hypothesis:**

Compared to etomidate, ketamine will show an improved hemodynamic profile in patients undergoing rapid sequence intubation.

STUDY DESIGN:

This study will be a prospective randomized controlled trial evaluating the hemodynamic response in adult patients (greater than or equal to 18 years of age) undergoing rapid sequence intubation (RSI).

STUDY SETTING:

This study will be a single-center study to include pre-hospital RSI performed by New Hanover Regional Medical Centers (NHRMC) emergency transport service providers as well as emergency medical physicians performing RSI at the NHRMC emergency department located on the main hospital campus.

STUDY POPULATION:

Adult patients age 18 and greater who are not pregnant and require rapid sequence intubation will be part of the study population. Patients may require rapid sequence intubation to secure his or her airway for a myriad of reasons to include trauma, impending respiratory failure, septic shock. These patients often have labile hemodynamics in the time period surrounding intubation and the drugs used may influence this hemodynamic response.

This study is projected to treat approximately 400 subjects. Our goal is to have 200 patients in the ED settings, with 100 having etomidate and 100 having ketamine. In the pre hospital setting there will be 100 having etomidate and 100 having ketamine.

ELIGIBILITY CRITERIA:**Inclusion Criteria:**

Adult patients age 18 and greater who require RSI for any indication.

Exclusion Criteria:

1. Children under the age of 18 as these patients have a different hemodynamic profile than adults and would require a separate study to clearly elucidate the effect of ketamine or etomidate during RSI.

2. Pregnant women of any age as these patients also have a different hemodynamic profile than adult patients and would require a separate study to clearly elucidate the effect of ketamine or etomidate during RSI.
3. Patients with a known hypersensitivity to ketamine or etomidate will not be administered that respective agent and will not be crossed over into the opposite group.

STUDY OUTCOMES:**Primary Outcomes:**

The primary outcome will be the incidence of post RSI hypotension between patients undergoing RSI with ketamine versus patients undergoing RSI with etomidate. Post RSI hypotension will be defined as a 20% decrease in the systolic blood pressure from a patient's baseline.

Secondary Outcome(s):

Secondary outcomes will include: incidence of first pass intubation success, incidence of supplemental blood pressure agents (e.g. vasopressors) required post-RSI, time to additional sedative use

STUDY PROCEDURES:**Recruitment of participants:**

Patients who require rapid sequence intubation are critically ill and are not capable of making medical decisions at the time of the procedure. During these critical moments, surrogate decision makers are rarely, if ever present and this procedure is performed as a life-saving measure to allow for further medical therapies. Informed consent of the patient nor a surrogate decision maker is possible at the time of the procedure.

Randomization:

Randomization will be assigned by calendar day beginning at midnight, with etomidate being administered to all RSI patients on even calendar days and ketamine being administered to all RSI patient on odd calendar days.

Study Procedure:

Etomidate will be dosed at a standard 0.3 mg/kg and ketamine will be dosed at a standard 2 mg/kg for the purposes of this study. Data will be collected from the pre-hospital electronic medical record for patients undergoing RSI in the pre-hospital setting and from the inpatient electronic medical record for patients undergoing RSI in the emergency department. Data extracted from each record will include ketamine or etomidate dosages and time of delivery, sets of vital signs prior to and post-intubation, number of intubation attempts, number of lost airways, dose and timing of any additional medications, requirement for additional fluid or blood product administration, indication for advanced airway placement, admitting service, lab data, past medical history, and standard patient demographics. The hemodynamic response will be measured by assessing hemodynamics for two measurements prior to administration of ketamine or etomidate and for two measurements up to fifteen minutes post administration or

until an additional sedative medication is administered. (Please separate sheet that will be placed in RedCap once IRB approval has been obtained).

Ketamine and etomidate are immediately available for RSI in the pre-hospital and hospital settings and are both currently standard of care for RSI at our facility.

Data Storage:

All data will be kept in the secure database RedCap. Only study staff will have access to the database.

Safety considerations/Patient safety:

Etomidate and ketamine are both frequently used in the pre-hospital and emergency department setting with an acceptable safety profile. Etomidate has described adverse reactions to include adrenal suppression, pain at the injection site, nausea and vomiting, and nystagmus. Ketamine has described adverse reactions to include confusion/delirium, hallucinations, vivid imagery, bradycardia, increased blood pressure, nausea and vomiting, pain at the injection site, laryngospasm and nystagmus. These adverse reactions have not precluded use in routine clinical care. If a patient has a known hypersensitivity or allergy to either medication, they will not be given that medication.

STATISTICAL CONSIDERATIONS AND DATA ANALYSIS:

Sample size and statistical power: To maintain 80% power with a probability of 0.05, 200 patients will be needed in each arm to detect at 25% difference in SBP (baseline to post drug administration effects)

Statistical methods:

Data will be analyzed using SPSS with a p-value of less than 0.05 being considered significant. We will consider a 20% decrease in systolic BP from a patient's baseline as significant, and will compare the incidence of post RSI hypotension between the two groups. Several a priori subgroups will be evaluated to include patients greater than 70 years of age, trauma patients requiring RSI, and those patients whose shock index is less than 0.9 versus those whose shock index is greater than 0.9.

OUTCOMES AND SIGNIFICANCE:

The results from this study will help elucidate a sedative agent that is most appropriate in unstable patients across a spectrum of clinical scenarios to include cardiac dysfunction, severe sepsis with septic shock, trauma and the elderly.

REFERENCES:

Bijker JB, van Klei WA, Kappen TH et al. Incidence of intraoperative hypotension as a function of the chosen definition. *Anesthesiology*. 2007;107:213-220.

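### As worded, exclusion item 3 acts only on the day's drug, so a hypersensitive patient's eligibility depends on assignment: a minor design flaw with a simple remedy

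*Combined protocol and SAP*

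**What the plan says.** The combined protocol and SAP deals with hypersensitivity in two places.

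- Exclusion Criteria, item 3: such patients "will not be administered that respective agent and will not be crossed over into the opposite group".
- Safety considerations/Patient safety: "If a patient has a known hypersensitivity or allergy to either medication, they will not be given that medication".

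The Randomization section assigns the drug by date, "with etomidate being administered to all RSI patients on even calendar days" and "ketamine being administered to all RSI patient on odd calendar days". The inclusion criterion is broad: "Adult patients age 18 and greater who require RSI for any indication".

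No section excludes a patient hypersensitive to either drug on both kinds of day. The statistical section defines no analysis set, and no section says how a patient who is not given the day's drug is recorded or analysed.

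**The concern.** Eligibility should rest on facts fixed before assignment and should exclude the same patients in both arms. Known hypersensitivity is such a fact, but item 3 lets it operate only when the allergen is the drug of the day. The population that can enter the etomidate arm includes ketamine-hypersensitive patients and not etomidate-hypersensitive ones; for the ketamine arm it is the other way round.

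If the two hypersensitive groups differ in frequency or in their risk of post-RSI hypotension, the arms would differ slightly even with no drug effect. Nothing later in the plan repairs this. The primary outcome compares patients by the drug with which they underwent RSI, so someone not given the day's drug has no stated place in the comparison.

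**Working it through.** **1. Reading the rule against the allocation**

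| Known hypersensitivity | Odd day (ketamine) | Even day (etomidate) |
|---|---|---|
| Ketamine | Not given ketamine, not moved to etomidate: out | No exclusion stated |
| Etomidate | No exclusion stated | Not given etomidate, not moved to ketamine: out |
| Neither | In | In |

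The first two rows differ by column, so eligibility depends on assignment.

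**2. Inputs for the size**

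The plan gives no figure on hypersensitivity, so there is none to reproduce. From the documents I take only 200 patients per arm. How that number was derived is a separate question and does not bear on this point. Everything else is assumed:

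- prevalence of known hypersensitivity: hK for ketamine, hE for etomidate, with no patient in both groups;
- hypotension risk: r in other patients, rK and rE in the two hypersensitive groups;
- no true drug effect.

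**3. Formula**

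- Etomidate arm risk = r + hK(rK − r)/(1 − hE)
- Ketamine arm risk = r + hE(rE − r)/(1 − hK)
- Spurious difference = hK(rK − r)/(1 − hE) − hE(rE − r)/(1 − hK)

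**4. Results**

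*Only one drug has hypersensitive patients* (hE = 0, hK = h; r = 30%, rK = 60%). The difference is h × 30 points. At 1% this is 0.01 × 30 = 0.3 points.

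*Extreme case* (hK = hE = h; one group at 100% risk, the other at 0%). The difference is h/(1 − h). At 1% this is 0.01/0.99 = 1.0 point.

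*Equal prevalence and equal risk* (hK = hE, rK = rE). The two terms cancel and the difference is 0.

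| h | One group only, 30-point gap | Extreme case | Equal groups |
|---|---|---|---|
| 0.1% | 0.03 points | 0.1 points | 0 |
| 0.5% | 0.15 points | 0.5 points | 0 |
| 1% | 0.3 points | 1.0 points | 0 |
| 2% | 0.6 points | 2.0 points | 0 |

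The extreme case shows that the bias cannot much exceed the prevalence itself.

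**5. Comparison with sampling error**

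At an assumed 30% event rate in both arms, the standard error of the difference is √(2 × 0.3 × 0.7/200) = 0.046, or 4.6 points. The 0.3-point bias is about one fifteenth of that (4.6/0.3 ≈ 15).

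**The case against.** **A blanket exclusion may have been meant.** Item 3 stands under Exclusion Criteria beside children and pregnant women, and no section says outright that a ketamine-hypersensitive patient is enrolled on even days. That is fair: enrolment on the other drug's days follows from the absence of any exclusion, not from a statement. But items 1 and 2 name excluded populations, whereas item 3 restricts a particular agent and bars a move to the other group, which makes little sense for someone already outside the study. If a blanket exclusion was intended, the same rewording is needed. The safety sentence is true under either reading and does not settle the matter.

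**The rule is symmetric.** Each arm loses its own hypersensitive patients and keeps the other's, so the effects can cancel. This stands. A reader might infer that the comparison as a whole is not like with like. The documents do not support that: they give no prevalence and no reason to expect a particular risk gap, and the net bias may be zero.

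**Selective charting.** A reader might also infer that item 3 lets staff who know the day's drug chart a doubtful reaction and so remove a patient from one arm. That opportunity comes mainly from allocation by calendar date, which is known in advance. It would remain after item 3 is reworded, so it belongs to the separate problem of predictable allocation and adds no weight here.

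**Conclusion.** The point holds as a minor design flaw. On its wording, item 3 makes eligibility depend on assignment, and no other section corrects this.

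It is not a demonstrated material bias. The net effect is bounded by roughly the prevalence of known hypersensitivity, which the documents do not give. It is about 0.3 points at an assumed 1% prevalence for one drug with an assumed 30-point risk gap, and zero if the two groups are alike in frequency and risk. The reason to change the rule is that a baseline exclusion should not depend on the arm and the change is cheap, not that the trial's conclusion is in danger.

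**What to change.** Reword item 3 so that patients with known hypersensitivity to either ketamine or etomidate, as documented before induction, are excluded from the study population and the analysis set on all days. Add two operating rules:

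- ascertain hypersensitivity to both drugs from the same record source on odd and even days;
- report these exclusions by odd and even day.

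The Randomization section, which gives the day's drug to every RSI patient, should be reconciled with the exclusion. The change concerns study eligibility only, not care.

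**Cost.** The record must be checked for both drugs in every patient. This matters because the data fields listed under Study Procedure include past medical history but do not name allergy status (the separate data sheet is not shown), and because patients cannot supply a history at the time. A few patients are lost. At an assumed prevalence of 0.1% to 2% per drug, 200/(1 − 2h) gives 201 (200/0.998, rounded up) to 209 (200/0.96, rounded up) screened per arm to leave 200 eligible.

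**Limit.** The rewording makes the rule-induced difference in eligibility zero. It does not prevent selective charting by staff who know the day's drug. Reporting by odd and even day might reveal it.

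### Allocation by odd/even calendar date is labelled randomization but has no chance element, and the plan does not say whether patients are analysed by assigned or received drug

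*Combined protocol and SAP*

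**What the plan says.** **Label.** STUDY DESIGN states: "This study will be a prospective randomized controlled trial evaluating the hemodynamic response in adult patients". The allocation rule stands under the heading Randomization.

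**Rule.** "Randomization will be assigned by calendar day beginning at midnight, with etomidate being administered to all RSI patients on even calendar days". Odd dates are assigned to the other drug. No random sequence, random start, concealment or blinding is described. The rule covers every RSI patient, and there is no consent step at the time of the procedure.

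**Motivation.** The background text says of earlier comparisons that "these studies have been retrospective in nature", and then: "A prospective, randomized trial is needed to determine the superiority of one induction agent over another".

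**Comparison groups.** STUDY OUTCOMES words the primary comparison as "patients undergoing RSI with ketamine versus patients undergoing RSI with etomidate". The Statistical methods paragraph refers only to two groups. No analysis set by assigned drug, by received drug or per protocol is named.

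**Departures from the day's drug.** The only rule concerns known hypersensitivity to an agent: such patients "will not be administered that respective agent and will not be crossed over into the opposite group". The Study Procedure section adds that both drugs are at hand in both settings and are standard care there.

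**Data.** "Data extracted from each record will include ketamine or etomidate dosages and time of delivery". A separate data sheet is mentioned but is not part of the documents.

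**The concern.** There are two separate points.

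First, the label. Randomization is the property that is meant to set this trial above the retrospective studies in the background text. Date parity does not supply it, because anyone with a calendar knows each assignment. A reader of the eventual report would credit the comparison with a protection that the design does not have.

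Second, the analysis groups. The plan expects the assigned and the received drug to coincide, and gives no analysis rule for when they do not. With both drugs available and no blinding described, a clinician could use the other day's drug. If that choice followed blood pressure and the patient were counted under the drug received, the groups would differ at baseline on the variable that defines the primary outcome, a 20% fall in systolic pressure. Leaving the rule open also allows the primary comparison to be defined after the data are seen.

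**Working it through.** **1. Label: passages side by side.** STUDY DESIGN says randomized. The Randomization section gives a rule that is fully determined by the date. The two cannot both stand, and no figure is needed to see it. The rule does not unbalance numbers: a 365-day year has seven 31-day, four 30-day and one 28-day month, so 7×16 + 4×15 + 14 = 186 odd days and 179 even days. With uniform arrivals, 400×186/365 ≈ 204 of 400 patients fall on ketamine days.

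**2. Bias if groups follow the drug received.** The documents give no event rates or switching shares, so every input here is assumed except the 200 per arm. There is no true drug effect, and each day type has 200 patients. Let q be the share with low systolic pressure, a the event risk in them, and 0.45 the risk in the rest. A fraction f of low-pressure patients on etomidate days receives ketamine.

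- Overall risk r = q·a + (1−q)·0.45; number moved m = 200·q·f
- Etomidate risk = (200r − a·m)/(200 − m)
- Ketamine risk = (200r + a·m)/(200 + m)

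Example with q = 0.30, a = 0.23, f = 0.50: r = 0.069 + 0.315 = 0.384 and m = 30. Etomidate risk = (76.8 − 6.9)/170 = 0.4112. Ketamine risk = (76.8 + 6.9)/230 = 0.3639. The spurious difference is 4.73 points.

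Type I error is for a two-sided pooled z-test at 0.05 (normal approximation), with se0 from the pooled risk and se1 from the separate risks: Φ((−1.96·se0 − d)/se1) + Φ((d − 1.96·se0)/se1).

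| q | a | f = 5% | 10% | 20% | 50% |
|---|---|---|---|---|---|
| 0.15 | 0.23 | 0.28 points, 5.0% | 0.56, 5.2% | 1.12, 5.6% | 2.82, 8.8% |
| 0.15 | 0.50 | −0.06, 5.0% | −0.13, 5.0% | −0.26, 5.0% | −0.64, 5.2% |
| 0.30 | 0.23 | 0.46, 5.1% | 0.92, 5.4% | 1.85, 6.7% | 4.73, 16.1% |

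The entries are etomidate minus ketamine risk in percentage points, then type I error. The sign depends on whether low-pressure patients have a lower or higher event risk than the rest, so even the direction cannot be derived from the documents. Grouped by the day's assigned drug, both groups have risk r and the spurious difference is 0 in every cell.

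**3. Power cost of analysing by assigned day.** The plan's 200 per arm cannot be reproduced uniquely, because it gives no event rates, standard deviation or sidedness. The effect is therefore varied. From an assumed 41.7% (r for q = 0.15, a = 0.23), the alternatives are 16.7% (25 points absolute), 28.4% (13.3 points, the difference detectable with 80% power) and 31.3% (25% relative, 0.75×41.7). With a share s switched in both directions, the difference shrinks to (p1 − p2)(1 − 2s).

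| Assumed rates | s = 0 | 10% | 20% |
|---|---|---|---|
| 41.7% vs 16.7% | above 99% | 99% | 91% |
| 41.7% vs 28.4% | 80% | 61% | 39% |
| 41.7% vs 31.3% | 58% | 41% | about 25% |

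(The last cell is 25.4% with the pooled null variance. With the unpooled variance it is 25.5%, which rounds to 26%.)

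In the middle row at s = 10%, for example, the difference is 13.33×0.8 = 10.66 points. For one-way switching the difference shrinks only by (1 − s). With 0.75 to 7.5% of etomidate-day patients switched (q·f for q = 0.15, f = 5 to 50%), power in the middle row is 79 to 74%.

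**The case against.** The rule is disclosed in full, so no reader of the protocol is misled about how days are assigned. It covers all RSI patients without a consent step, so foreknowledge has little enrolment decision to act on. No passage suggests that odd and even dates differ in prognosis. The bias figures describe off-schedule drug use, which could also occur under a random list, so they say nothing about the label. A date rule that needs no lookup is defensible in ambulances and emergency departments.

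Most of this stands, and it lowers the severity. It does not make the label correct: disclosing the rule does not introduce chance, and the term would carry over into the report. Nor does it settle how off-schedule patients are analysed. The hypersensitivity rule covers one reason and concerns administration. The unseen data sheet may record the assigned drug, but a recorded variable is not an analysis rule.

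Stronger readings are tempting, and the documents do not support them:

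- **Clinicians can choose who enters each arm.** The all-comers rule leaves little room for that.
- **Selective switching will occur.** The background text reports a trend to lower systolic pressure after etomidate in trauma and elderly patients, which could be a motive. Nothing shows that clinicians would act on it.
- **The background text mislabels this trial.** It states that a randomized trial is needed, which is a separate statement.

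**Conclusion.** The label is wrong as written: this is quasi-random allocation. That conclusion rests on the text alone. The missing analysis rule is a real but modest gap. Bias is possible, not shown. Under the assumed inputs, type I error stays between 5.0 and 6.7% when up to 20% of low-pressure patients are switched one way. The 16.1% figure needs 30% of patients with low pressure and half of them switched, and should not be read as an expected value. A reader might also infer that the primary result is invalid or that the plan must not proceed as it stands. The documents do not support that for a disclosed rule applied to all comers. Severity: below must-fix.

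**What to change.** 1. **Relabel.** In STUDY DESIGN and under Randomization, call the design quasi-randomized, with allocation by alternate calendar date, and report the conclusions as those of a quasi-randomized trial. Leave the background statement of need unchanged. This costs wording only.

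2. **Define the primary analysis set.** Analyse all eligible RSI patients by the drug assigned to the calendar day, and report drug received as a sensitivity analysis. Fix the day by one recorded time that exists for every patient and is not open to choice, for example the recorded start of the RSI encounter. Drug-delivery time is unsuitable, because a patient given neither drug has none and because it can shift around midnight. Apply the hypersensitivity exclusion to the analysis set in the same way on both day types. The received drug is already extracted and the date gives the assigned one, so the new data are about one timestamp. Because the outcome measurements are timed from administration, the plan should also say how an eligible patient given neither drug is handled. The price is dilution if switching is common, and its size depends on the true effect, as the power table shows. Analysis by drug received avoids that loss, but is unbiased only if switching is unrelated to outcome.

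3. **Report by day type** the number of RSI patients, baseline systolic pressure and the share given the off-schedule drug. This costs one table.

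**Optional.** A computer-generated list of drug days would make the word randomized true. The days would then be the randomized clusters, the teams would need a daily lookup, and same-day switching would still be possible. It is a trade-off and not a required change.

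### Do separate source records for pre-hospital and ED patients leave post-RSI vasopressor use and time to additional sedative without a common meaning?

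*Combined protocol and SAP*

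**What the plan says.** All the relevant text is in the combined protocol and SAP.

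- **Source of data (Study Procedure).** The rule for the transport setting is "Data will be collected from the pre-hospital electronic medical record for patients undergoing RSI in the pre-hospital setting". For the other setting the source is different: "from the inpatient electronic medical record for patients undergoing RSI in the emergency department". Nothing says whether a pre-hospital patient's hospital record is also consulted.
- **Items to extract (Study Procedure).** One list serves both settings: "Data extracted from each record will include ketamine or etomidate dosages and time of delivery". It goes on to "dose and timing of any additional medications" and, later in the same list, "indication for advanced airway placement, admitting service, lab data, past medical history, and standard patient demographics".
- **Outcomes (Secondary Outcome(s)).** Besides first-pass success, the section lists "incidence of supplemental blood pressure agents (e.g. vasopressors) required post-RSI, time to additional sedative use". Neither of these two has an end of follow-up or a censoring rule.
- **The only time limit (Study Procedure).** Hemodynamics are taken "for two measurements up to fifteen minutes post administration"; the alternative stopping point is given as "until an additional sedative medication is administered". This limit applies to the vital-sign readings and not to the two secondary outcomes.
- **Numbers and allocation (Study Population; Randomization).** About 400 patients are planned: 200 in the ED and 200 pre-hospital, with 100 per drug in each. The drug alternates by calendar day for all RSI patients.
- **Analysis (Statistical methods).** A comparison is specified for the incidence of hypotension. None is specified for the two secondary outcomes, and setting is not mentioned.

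The Study Procedure section also refers to a separate data sheet to be placed in RedCap. It is not among the documents available here.

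**The concern.** An event rate needs a period at risk, and a time-to-event outcome needs a rule for patients in whom the event is not seen. If the source sentence is taken literally, a pre-hospital patient is observed until the transport record closes, while an ED patient is observed for as long as the inpatient record runs. A vasopressor started an hour after induction would then count in the ED and be invisible in a pre-hospital patient. A combined rate would average two different periods. For time to sedative, many pre-hospital patients would have no recorded time, and the plan does not say whether they are censored, missing or event-free.

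Two of the three secondary outcomes are affected, in up to half of the planned patients. If the drug also changed when events occur relative to hand-off, capture could differ between arms as well.

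**Working it through.** The documents give no vasopressor rate, sedation time, transport time or hand-off time. The plan has no figure on this point to reproduce. The arithmetic below rests on assumed inputs; only the 200/200 split and the 100 per drug per setting come from the protocol.

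**1. Combined vasopressor rate.** Let the true rate over one common window be p = 0.25, with complete capture in the ED and a fraction c of pre-hospital starts falling before hand-off. The pre-hospital rate is pc. With equal halves, the combined rate is p(1 + c)/2.

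| c | Pre-hospital | Combined |
|---|---|---|
| 0.3 | 7.5% | 16.25% |
| 0.5 | 12.5% | 18.75% |
| 0.7 | 17.5% | 21.25% |

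Under the literal reading, the overall rate would be understated by 3.75 to 8.75 points.

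**2. Time to sedative.** With exponential times and median m, the share with no recorded time at hand-off h is 2^(−h/m). For m = 20 minutes:

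- h = 15: 2^(−0.75) = 0.595, about 119 of 200.
- h = 30: 2^(−1.5) = 0.354, about 71 of 200.
- h = 45: 2^(−2.25) = 0.210, about 42 of 200.

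These are censored observations. If the record ends at a time unrelated to the patient's need for sedation, an ordinary survival analysis handles them. The outcome keeps its meaning, and some patients contribute shorter follow-up.

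**3. Comparison of the drugs.** With equal true rates, capture c1 and c2 in the pre-hospital halves of the two arms, and the planned equal mix of settings, the spurious difference is p(c1 − c2)/2. If c1 = c2 it is 0. A non-zero value requires capture to differ by drug, and nothing in the documents indicates that.

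**4. Power.** Take true rates of 30% and 20% with 200 per arm; power is 64%.

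- If half of pre-hospital starts are missed in each arm, the combined rates are 0.75 × 30% = 22.5% and 0.75 × 20% = 15%, and power is 48%.
- If instead 10 points are missed in the pre-hospital half of each arm (5 points per arm overall), the rates are 25% and 15%, and power is 71%.

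The direction depends on the assumption, so no loss of power is shown.

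**5. Reading the passages together.** The source sentence, taken alone, gives one record per patient. The extraction list, which applies to each record, asks for admitting service and laboratory data. A patient's admitting service is settled at the hospital. The Study Setting section describes one centre whose own transport service performs the pre-hospital intubations. These points favour the reading that hospital data were meant to be available for pre-hospital patients, although they do not prove it.

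**6. Whether an explicit rule is sure to help.** A natural rule for patients without a hospital record is to count vasopressor starts before hand-off as events and set everyone else to missing. In a complete-case analysis, every such patient retained is then an event. With p = 0.25, c = 0.5 and U unlinked patients among 400, the rate is [0.25(400 − U) + 0.125U] / [(400 − U) + 0.125U].

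- U = 100: (75 + 12.5)/(300 + 12.5) = 28.0%.
- U = 200: (50 + 25)/(200 + 25) = 33.3%.

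The true value is 25%, so this rule replaces an understatement with an overstatement.

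**The case for a change.** The strongest case for a change is that the gap survives either reading. Even if hospital records are used for everyone, a post-RSI period without an end is not a defined window, and RedCap as common storage does not link records. Protocol text should not depend on a data sheet that readers cannot see. The remedy looks cheap: a few sentences, and one further chart lookup for up to 200 patients. The sedation time also ends the hemodynamic window, so an early hand-off might affect the primary outcome.

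Part of this stands. The linkage, the window and the censoring rule are not written down, and a reader of the results should be told what period they cover.

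The rest is weaker. That observation stops at hand-off is an inference, because the protocol never mentions hand-off or says when the transport record closes. The extension to blood pressure needs hand-off within fifteen minutes, and transport times are not given. The background section reports the investigators' earlier pre-hospital study at this centre, which compared systolic pressure from before RSI to fifteen minutes after it. Readings over that interval were therefore obtained for pre-hospital patients there, although the record used is not named. The effort of matching records is not described in the documents, so the claim of low cost is also an assumption.

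**Conclusion.** No change to the plan follows. This is missing detail that analysts can fill sensibly: use whichever records cover the patient, apply one window from induction in both settings, treat both outcomes as time to first event with censoring at the end of the available record, and report how many patients in each arm lack a hospital record. The planned design does not prevent any of this.

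The gap touches two of three secondary outcomes and up to 200 of about 400 patients. On the literal reading and assumed inputs, it would lower a 25% overall vasopressor rate by 3.75 to 8.75 points. It creates no difference between the drugs unless capture differs by arm, and its effect on power could go either way. This conclusion rests on the extraction list meaning what it appears to mean, on the planned balance of drugs within each setting being roughly achieved, and on record end being unrelated to the drug given. If the transport record alone were used and capture clearly differed by drug, the two secondary results would need a caution when reported.
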